9.3. Data Analysis Considerations

There will be 4 fMRI and 3 MRS data points as shown in the table below:

Treatment Period ^a			Albiglutide	Exenatide
Day Relative to Period Start ^b	1 Off-therapy	1 Off-therapy	8 At T-max	8 At T-max
Visual Nauseogenic Task	No	Yes	No	No
MRI Data Point (DP)	DP1	DP2	DP3	DP4

Treatment Period ^a			Albiglutide	Exenatide
Resting State BOLD fMRI	✓		✓	✓
Nauseogenic task based BOLD fMRI		✓		
ASL	✓		✓	✓
MRS	✓		✓	✓

^a The order of the treatment periods will be randomized.

^b The day is relative to start of the Treatment Period.

For each subject, the Off-therapy Day 1 assessment(s) (DP1 and/or DP2 in table above) during the dosing/imaging sessions will serve as the baseline fMRI assessment.

Nauseogenic task BOLD signal (DP2,) will be assessed only during the off-therapy fMRI session. For the BOLD endpoint, the main contrasts of interest are the differences in the connectivity between albiglutide and off-therapy (DP3-DP2), between Exenatide and off-therapy (DP4-DP2), and between Albiglutide and Exenatide (DP3-DP4).

For resting state analysis rCBF ASL endpoints, the contrasts of interest are the differences DP3-DP1, DP4-DP1, and DP4-DP3. Similarly, for GABA and Glutamate concentrations, the main contrasts of interest are the differences DP3-DP1, DP4-DP1, and DP4-DP3.

The vection-induced nausea will provide a reference to regions of nausea associated brain activity. A group map will be calculated as in the previous Martinos Center study, and regions of interest (ROI) will be defined from the group map. These ROIs will then be used to perform masked comparison analyses for rCBF and MRS (where possible) data between the albiglutide vs exenatide and drug vs no-drug conditions. Such targeted analyses will allow for greater power than whole brain analyses which will need to be more stringently corrected for multiple comparisons.

There will be no imputation for missing data. Subjects who only partially complete the study may be included in some of the analyses where appropriate, depending on which data are available and which are missing.

Summary statistics (including number of subjects, mean, median, min, max, SD, SE) will be reported for continuous variables. The frequency and percentage will be used to summarize categorical variables.

Functional MRI Data

Pre-processing steps will include motion correction carried out by sequentially aligning each time-point across the series with a single target scan, using a rigid-body registration algorithm. Further pre-processing steps may also include slice timing corrections and

spatial smoothing. To ensure each subject's parameter estimate maps (e.g. following general linear modeling, see below) lie in a common anatomical space, an initial affine registration will be applied from the native low-resolution Echo Planar Imaging (EPI) data to the respective high resolution T1-weighted scan or a mean image of EPI scans. These spatially normalized subject-specific statistics will then undergo a further alignment onto a common atlas space such as the Montreal Neurological Institute (MNI) coordinate system.

Following pre-processing, several sets of statistical analyses will then be conducted, with standard methods (e.g. application of the General Linear Model, Independent Components Analysis) with the addition of sophisticated noise-modeling methods, derived from the acquired physiological data (respiratory/cardiac). Data will be examined at both a whole-brain and regions of interest (ROI) level, with ROIs defined by intersecting anatomical label masks (based on standard atlases such as the well known Harvard-Oxford Atlas) with clusters derived from the group data. Other exploratory methods, such as Multi-Voxel Pattern Analysis (MVPA) may also be employed, as appropriate. Analyses will take advantage of individual subject nausea rating responses during stimulation, for both stimulus-based (distinct windows), and percept based (increasing nausea transitions) analyses, as in previous publications [[name], 2013]. Results from the off-therapy motion sickness task fMRI scan will be used to define ROI's of nausea-related brain circuitry in the same individuals who will also experience on-therapy nausea MRI scanning. These ROI's will be used to guide analysis of the fMRI, ASL, and MRS data from both on-therapy and off-therapy scan sessions. Group analyses will include both the entire on-drug group and, in a separate analysis, the subgroup of subjects who were on-drug and perceived nausea during the scan. This will allow for an investigation of sub-threshold changes in brain physiology due to the drug as well as more specific analyses targeting nausea perception as a result of drug intake.

Arterial spin labeling (ASL) data will be pre-processed similarly for motion correction, and tagged and un-tagged images will be subtracted and used to calculate regional cerebral blood flow (rCBF) using validated equations for pulsed continuous ASL (pCASL). ASL data acquired while the subject was experiencing nausea will then be contrasted with nausea-free scans acquired at the beginning of the Off-therapy MRI session (i.e. before thevection nausea task), to evaluate brain rCBF response during drug-induced nausea perception.

9.3.1. Analysis Populations

For this exploratory study, the analysis set will include subjects who have valid data.

9.3.2. Part A Data Review

There are 2 potential interim data reviews during the study. The first interim data review will be performed after all MRI assessments from 4 subjects have been collected and cleaned. Based on results from interim review, a decision to randomize 4 more subjects for Part A, and/or adjust Part B design (e.g., change in MRS pulse sequence), will be made based on imaging evaluators' judgment in consultation with the PI and Sponsor.

A second interim data review will occur only if a decision to randomize 4 more for Part A is made after initial review of results from the first 4 subjects. This second review, should it occur, will use all data from 8 subjects. Once the required number of subjects has been randomized for an upcoming data review, randomization of additional subjects will be put on hold. Randomization will resume after a decision to continue the study is made.

9.4. Key Elements of Analysis Plan

Data from Parts A and B, as appropriate, will be pooled for final analysis. For comparisons between Albiglutide and exenatide, analysis of variance (ANOVA) will be used to analyze quantifiable endpoints with treatment and period as fixed effects, and subject as random effect. The contrast of interest for BOLD, ASL and MRS endpoints described in Section 9.3 will be tested using this model.

Pearson's and Spearman's correlation coefficients will be used to review relationships between selected quantifiable end points.

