Data from Parts A and B will be pooled, as appropriate, for final analysis. For comparisons between albiglutide and exenatide, analysis of variance (ANOVA) will be used to analyze quantifiable endpoints with treatment and period as fixed effects, and subject as random effect. Pearson's and Spearman's correlation coefficients will be used to review relationships between selected quantifiable end points. A minimum of four subjects will be enrolled and analyzed in Part A (Cohort 1). Based on the results, a decision to enroll 4 additional subjects could be taken (Cohort 2). The criteria for this decision will be based on clinical (e.g., safety) and technical judgment after review of the neuroimaging data. Changes in brain activity associated with exenatide or albiglutide in imaging modalities tested will inform progression, methods, and analysis plan to Part B. For each subject adverse events will be reviewed by the Medical Monitor in both Parts A and B prior to the next subject being studied. Data analysis for Part A and Part B will be exploratory. The analysis plan for Part B will be finalized based on Part A results.

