In both Part A and Part B, subjects who meet the eligibility criteria will be randomized in a crossover fashion to one of 4 different sequences, each consisting of two dosing/imaging sessions (Session 1 and Session 2) separated by a 6-9-week washout period (Section 4.2 Table 1). Each subject will undergo a single off-therapy MRI during a separate Visit according to the randomization sequence to minimize the total number of scans per subject. The timing or sequencing of the off-therapy MRI will be randomized (i.e. Session 1 or Session 2) to account for potential learning effects. Each subject will undergo one off-therapy MRI, one post-dose albiglutide MRI and one post-dose exenatide MRI for a total of 3 MRI scans during the study. The visit schedule is set to allow the Off-therapy MRI scan visit to occur approximately 7 days prior to the post-dose scan within the Session as this is the minimal recommended time between scans. The visit on Day 5 allows the dosing of albiglutide or albiglutide placebo to occur 4 ± 1 days before the post-dose MRI i.e., at estimated T_{max} (3-5 days). Because of the short T_{max} (2 hrs) for exenatide, exenatide or saline placebo is given on the day of the MRI scan (Day 8). Therefore, MRI Session 1 and Session 2 each consist of 2 or 3 single-day out-patient visits according to the randomization schedule on the following days:

- Day 1 (Either Session 1 or 2 per randomization) for an off-therapy MRI scan consisting of resting-state fMRI, a nauseogenic task fMRI, ASL and MRS and nausea associated assessments,
- Day 5 for a single dose of 50 mg albiglutide or albiglutide placebo, and
- Day 8 for a single dose of 10 μ g exenatide or saline placebo followed by a post-dose MRI scan consisting of resting-state fMRI, ASL and MRS, and nausea associated assessments.

Subjects will be blindfolded when receiving the study medication injection to maintain the single-blind.

For all MRI sessions, subjects must fast overnight and will be instructed to refrain from eating and drinking anything but water starting at approximately 10 pm the night before or with in 8 hours of the start of their MRI appointment.

For the off-therapy session, MRI scan and nausea associated assessments will be conducted without prior injection (no drug, no placebo).

On post-dose scanning visits, subjects will be offered a meal after the procedure before leaving the unit, and capillary glycemia will be assessed.

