9.1. Hypotheses

No primary hypothesis will be pre-specified due to the exploratory nature of the study.

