9.2. Sample Size Considerations

A total from Parts A and B of 24 or 28 randomized subjects with valid MRI data that could be pooled for analysis will be targeted for the entire study. Part A will initially randomize 4 subjects. Based on data review from the initial 4 subjects, additional 4 subjects may be randomized for Part A. The decision to enroll another Cohort of 4 subjects in Part A will be based on imaging evaluators' judgment in consultation with the PI and Sponsor.

Part B will randomize 20 subjects.

Subjects will be randomized according to treatment sequences described in Section 4.2.

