9.2.1. Sample Size Assumptions & Size Sensitivity

Accurate prospective determination of experimental power and sample size is difficult for fMRI experiments because many idiosyncratic factors (e.g. scanner sequence, brain region under investigation, task paradigm) can have a large influence on the effective signal-to-noise. In addition, there is little similar published work available to act as a guide. A target sample size in the range 12 to 24 is recommended by Desmond and Glover [Desmond, 2002] for fMRI experiments; though it should be noted that advances in acquisition technology and analysis techniques in the last thirteen years have significantly increased signal-to-noise, meaning the upper bound of the estimate ($N \approx 24$) may now be somewhat inflated. Importantly, the sample size chosen for this study is consistent with the sample size previously published by the Martinos Center group in their nausea neuroimaging study [[name], 2013].

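### The planned albiglutide–exenatide ANOVA omits the randomised session of the off-therapy scan: a small loss of precision, and bias only under a particular pattern of losses

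*Protocol*

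**What the plan says.** Table 1 (Protocol 4.2) crosses two randomised factors: drug order, and the session that holds the single off-therapy visit. Protocol 4.1 gives the reason for the second: "The timing or sequencing of the off-therapy MRI will be randomized (i.e. Session 1 or Session 2) to account for potential learning effects". The off-therapy scan comes about 7 days before the drug scan of its session.

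The analysis model in Protocol 9.4 is "analysis of variance (ANOVA) will be used to analyze quantifiable endpoints with treatment and period as fixed effects, and subject as random effect". The synopsis repeats it: "with treatment and period as fixed effects, and subject as random effect". Section 9.4 adds: "The contrast of interest for BOLD, ASL and MRS endpoints described in Section 9.3 will be tested using this model". No term for off-therapy session, scan order or sequence appears in the Protocol or the SAP.

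The pooled analysis was to rest on "A total from Parts A and B of 24 or 28 randomized subjects with valid MRI data". Replacements go to the same sequence, but replacement is discretionary (4.3, 9.2.2). Only valid data are analysed (9.3.1), and missing data are not imputed (9.3).

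**The concern.** A factor that is randomised because it may matter would normally appear in the model. Here it has a definite link to the primary between-drug contrast. In every subject exactly one of the two drug scans shares a session with the off-therapy visit: albiglutide in sequences 1 and 4, exenatide in sequences 2 and 3. If having had that visit changes the drug scan, the change enters the within-subject drug difference with a sign that depends on sequence, and the model has nothing to absorb it. At stake are the width of the albiglutide–exenatide interval and, if sequences are lost unequally, the estimate itself.

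**Working it through.** **Inputs from the documents.** Scan orders from Table 1 (A albiglutide, E exenatide, Off off-therapy): sequence 1 Off‑A‑E, 2 A‑Off‑E, 3 Off‑E‑A, 4 E‑Off‑A. Total N is 24 or 28, which agrees with the parts: 4 + 20 = 24 and 8 + 20 = 28. The Protocol has no power or precision calculation to reproduce. The sample size rests on published guidance ("A target sample size in the range 12 to 24 is recommended") and on consistency with an earlier nausea imaging study.

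**Assumptions.** Equal allocation (six per sequence at N = 24; the ratio is not stated), two valid drug scans per subject, a two-sided 95% interval, and SD of the within-subject difference D = A − E set to 1. The documents give no size for a learning effect, so a range is shown. Only the two drug scans are modelled, not off-therapy as a third treatment level.

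**Model in terms of D.** With complete pairs, the 9.4 model regresses D on drug order. The A − E estimate is the average of the two order-specific means of D, with SE = 1/√N when the orders are equal in size. Learning from Session 1 to Session 2 that is the same for everyone is the period effect and drops out.

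**Two forms of effect.**
- Same-session effect v, gone by the next session: D shifts by +v in sequences 1 and 4, and by −v in 2 and 3.
- Persistent effect λ on every scan after the off-therapy scan: it cancels in sequences 1 and 3, where both drug scans follow. It shifts D by −λ in sequence 2 and +λ in sequence 4. Period absorbs half, leaving ±λ/2, so λ acts like v = λ/2.

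**Width, balanced sequences.** The shifts average to zero across sequences, so the bias is 0. They add Nv² (or Nλ²/4) to the residual sum of squares on N − 2 df:

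expected residual variance = 1 + [N/(N − 2)]·v², or 1 + [N/(N − 2)]·λ²/4.

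Half-width without the term = t(0.975, N − 2)·√(residual variance)/√N. With the term it is t(0.975, N − 3)/√N. At N = 24 the latter is 2.0796/√24 = 0.4245. With no effect, the 9.4 half-width is 2.0739/√24 = 0.4233.

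| Effect (SD of D) | Persistent: 9.4 half-width | Wider by | Same-session: 9.4 half-width | Wider by |
|---|---|---|---|---|
| 0.3 | 0.4285 | 0.9% | 0.4436 | 4.5% |
| 0.5 | 0.4375 | 3.1% | 0.4776 | 12.5% |
| 0.7 | 0.4507 | 6.2% | 0.5244 | 23.5% |

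Worked case, v = 0.5: 1 + (24/22)(0.25) = 1.2727; 0.4233 × √1.2727 = 0.4776; 0.4776/0.4245 = 1.125. At N = 28 the adjusted half-width is 0.3892. An effect of 0.5 gives 0.4013 (+3.1%) if persistent and 0.4376 (+12.4%) if same-session. The break-even persistent effect is about 0.14 at N = 24 and 0.12 at N = 28; below it the added term does not shorten the interval.

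The sampling error of the balanced estimate is unaffected, because the shifts cancel; only its estimated SE is inflated. Simulated coverage was 95.8% at λ = 0.5 and 97.0% at λ = 1.0 (equivalently v = 0.5).

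**Bias, unequal losses.** Let p2 and p4 be the shares with off-therapy in Session 2 among A-first and E-first completers: p2 = n2/(n1 + n2), p4 = n4/(n3 + n4). Then

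bias = v·(p4 − p2), or (λ/2)·(p4 − p2).

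| Completers, sequences 1/2/3/4 | p4 − p2 | Same-session | Persistent |
|---|---|---|---|
| 6/4/4/6 | 0.6 − 0.4 = 0.20 | 0.20v | 0.10λ |
| 6/5/6/6 | 0.500 − 0.455 = 0.045 | 0.05v | 0.02λ |
| 4/4/6/6 | 0.5 − 0.5 = 0 | 0 | 0 |

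**Effect of the added term.** A same-session indicator on each drug scan removes both the extra residual and the bias, for either form. Under 6/4/4/6 it raises the variance of the estimate by 1/(1 − 0.20²) = 1.042. A subject-level main effect of off-therapy session changes nothing, because it is constant within subject and drops out of D.

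**The case against.** The case against changing anything is substantial. Randomising and counterbalancing the scan is itself a way of accounting for learning, and with balanced sequences the 9.4 interval is valid, merely conservative. The Protocol speaks only of potential effects and does not say that they reach the drug scans. Those scans contain no vection task (7.3.1), and every subject has already met the stimulus in the mock scanner (7.2.3). Same-sequence replacement limits imbalance, and 6/4/4/6 needs four unreplaced losses in two particular sequences. The study is exploratory ("No primary hypothesis will be pre-specified due to the exploratory nature of the study"), and the between-drug ANOVA is not in the SAP: Part B was cancelled, four subjects completed, and SAP 2.1 drops their group analysis.

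All of this stands and sets the severity. It does not remove the mismatch in the Protocol's own plan: the factor was thought important enough to randomise, the analysis set admits only valid scans, and replacement is discretionary.

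A reader might infer that any learning effect distorts the drug comparison, or that any imbalance biases it. Neither follows. Common learning goes into period, and 4/4/6/6 gives no bias in the two-scan fit. Nor should the larger widths be read as the expected loss: they assume that the effect has gone by the next session, whereas learning that lasts gives the smaller ones.

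**Conclusion.** The omission is real and minor. For the planned 24 or 28 subjects it costs some precision if the off-therapy scan alters a subject's two drug scans differently. For effects of 0.3 to 0.7 SD the 95% interval is 0.9% to 6.2% wider if the effect persists, and 4.5% to 23.5% wider if it is confined to the same session. Bias arises only when the off-therapy split differs between drug orders. In the cases tried it was at most 0.10 of a persistent effect or 0.20 of a same-session effect, and about 0.02 or 0.05 after losing one subject.

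These figures rest on assumed equal allocation, complete drug-scan pairs and an effect size that the documents do not supply. They concern albiglutide versus exenatide only, not the drug versus off-therapy contrasts. The documents do not support reading this as a flaw in reported results, since the SAP does not run this ANOVA.

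**What to change.** In Protocol 9.4 and the synopsis, for the planned pooled analysis of 24 or 28 subjects, add one fixed effect at the level of the drug scan: off-therapy scan in the same session (yes/no), alongside treatment and period. This is equivalent to off-therapy session × period. State that it is not a subject-level main effect, which would do nothing.

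Cost: one sentence and one residual degree of freedom. If there is no effect, the interval at N = 24 is about 0.3% wider (0.4245 against 0.4233). Under 6/4/4/6 the variance rises by about 4%. No new data are needed.

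Do not apply the term to the four Part A subjects alone. Assuming one per sequence, residual df would fall from 2 to 1 and the 95% t multiplier would rise from 4.30 to 12.71.

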10. STUDY GOVERNANCE CONSIDERATIONS

10.1. Posting of Information on Publicly Available Clinical Trial Registers

Study information from this protocol will be posted on publicly available clinical trial registers before enrollment of subjects begins.

10.2. Regulatory and Ethical Considerations, Including the Informed Consent Process

Prior to initiation of a site, GSK will obtain favourable opinion/approval from the appropriate regulatory agency to conduct the study in accordance with International Conference on Harmonisation (ICH) Good Clinical Practice (GCP) and applicable country-specific regulatory requirements.

The study will be conducted in accordance with all applicable regulatory requirements, and with GSK policy.

The study will also be conducted in accordance with ICH GCP, all applicable subject privacy requirements, and the guiding principles of the current version of the Declaration of Helsinki. This includes, but is not limited to, the following:

- IRB/IEC review and favorable opinion/approval of the study protocol and amendments as applicable
- Obtaining signed informed consent
- Investigator reporting requirements (e.g. reporting of AEs/SAEs/protocol deviations to IRB/IEC)

- GSK will provide full details of the above procedures, either verbally, in writing, or both.
- Signed informed consent must be obtained for each subject prior to participation in the study
- The IEC/IRB, and where applicable the regulatory authority, approve the clinical protocol and all optional assessments, including genetic research.
- Optional assessments (including those in a separate protocol and/or under separate informed consent) and the clinical protocol should be concurrently submitted for approval unless regulation requires separate submission.
- Approval of the optional assessments may occur after approval is granted for the clinical protocol where required by regulatory authorities. In this situation, written approval of the clinical protocol should state that approval of optional assessments is being deferred and the study, with the exception of the optional assessments, can be initiated.

10.3. Quality Control (Study Monitoring)

- In accordance with applicable regulations including GCP, and GSK procedures, GSK monitors will contact the site prior to the start of the study to review with the site staff the protocol, study requirements, and their responsibilities to satisfy regulatory, ethical, and GSK requirements.
- When reviewing data collection procedures, the discussion will also include identification, agreement and documentation of data items for which the eCRF will serve as the source document.

GSK will monitor the study and site activity to verify that the:

- Data are authentic, accurate, and complete.
- Safety and rights of subjects are being protected.
- Study is conducted in accordance with the currently approved protocol and any other study agreements, GCP, and all applicable regulatory requirements.

The Investigator and the head of the medical institution (where applicable) agrees to allow the monitor direct access to all relevant documents

